### ***Management of Adverse Experiences***

As above, weight gain would not be considered an adverse event. Weight loss will be managed by increasing the target calorie goal by 235 Kcal/day or more as measured empirically. Gastrointestinal side effects will be managed by adding over-the counter simethicone, fiber

(psyllium, cellulose, wheat dextrin), or by removing possible culprit foods such as dairy, wheat. Gastroesophageal reflux will be managed with over-the counter calcium carbonate, or if ineffective, prescription medications at the discretion of the treating physician.

Table 3. Adverse Events by Body Sytem	Type	Cntl		HC/HC		HF/HC		p values (events)			p values (% Pts)		
		N	Pts (%)	N	Pts (%)	N	Pts (%)	Overall	HC/HC vs. Cntl	HF/HC vs. Cntl	Overall	HC/HC vs. Cntl	HF/HC vs. Cntl
Allergy/Immunology (Allergic rhinitis)	AE	0	0 (0)	1	1 (13)	0	0 (0)	0.81	0.69	>0.99	>0.99	>0.99	>0.99
	SAE	0	0 (0)	0	0 (0)	0	0 (0)	>0.99	>0.99	>0.99	>0.99	>0.99	>0.99
Cardiac (Atrial fibrillation, elevated troponin)	AE	2	1 (17)	0	0 (0)	0	0 (0)	>0.99	0.97	0.97	0.6	0.43	>0.99
	SAE	0	0(0)	0	0 (0)	0	0 (0)	>0.99	>0.99	>0.99	>0.99	>0.99	>0.99
Constitutional Symptoms (Fatigue, weight change)	AE	7	2 (33)	2	2 (25)	5	2 (33)	0.41	0.2	0.78	>0.99	>0.99	>0.99
	SAE	0	0 (0)	0	0 (0)	0	0 (0)	>0.99	>0.99	>0.99	>0.99	>0.99	>0.99
Dermatology (Abrasion)	AE	0	0 (0)	0	0 (0)	1	1 (17)	0.71	>0.99	0.51	0.6	>0.99	>0.99
	SAE	0	0 (0)	0	0 (0)	0	0 (0)	>0.99	>0.99	>0.99	>0.99	>0.99	>0.99
Gastrointestinal (detached feeding tube, bloating, dyspepsia, diarrhea)	AE	13	6 (100)	8	4 (50)	21	6 (100)	0.04	0.11	0.21	0.02	0.09	>0.99
	SAE	0	0 (0)	0	0 (0)	0	0 (0)	>0.99	>0.99	>0.99	>0.99	>0.99	>0.99
Hematology/Coagulation (Thrombocytopenia)	AE	1	1 (17)	0	0 (0)	0	0 (0)	>0.99	0.97	0.64	0.6	0.43	>0.99
	SAE	0	0 (0)	0	0 (0)	0	0 (0)	>0.99	>0.99	>0.99	>0.99	>0.99	>0.99
Infection (Urinary tract, pneumonia)	AE	5	2 (33)	3	3 (38)	6	4 (67)	0.46	0.41	0.82	0.62	>0.99	0.57
	SAE	1	1 (17)	0	0 (0)	0	0 (0)	0.6	0.43	>0.99	0.6	0.43	>0.99
Metabolic/Laboratory (Elevated alkaline phosphatase, hypokalemia)	AE	2	1 (17)	0	0 (0)	0	0 (0)	>0.99	0.97	0.97	0.6	0.43	>0.99
	SAE	0	0 (0)	0	0 (0)	0	0 (0)	>0.99	>0.99	>0.99	>0.99	>0.99	>0.99
Musculoskeletal (Falls, weakness)	AE	0	0 (0)	5	1 (13)	4	2 (33)	>0.99	0.97	0.97	0.45	>0.99	0.45
	SAE	0	0 (0)	0	0 (0)	0	0 (0)	>0.99	>0.99	>0.99	>0.99	>0.99	>0.99
Neurology/Psychiatry (Dizziness, depression)	AE	1	1 (17)	1	1 (13)	1	1 (17)	0.97	0.9	0.99	>0.99	>0.99	>0.99
	SAE	0	0 (0)	0	0 (0)	1	1 (17)	0.6	>0.99	>0.99	0.6	>0.99	>0.99
Pain (Abdomin, neck, limb)	AE	3	2 (33)	2	2 (25)	4	3 (50)	0.58	0.46	0.72	0.84	>0.99	>0.99
	SAE	2	1 (17)	0	0 (0)	0	0 (0)	0.18	0.18	0.5	0.6	0.43	>0.99
Pulmonary/Upper Respiratory (Dyspnea, hypoxia, aspiration, cough)	AE	8	3 (50)	1	1 (13)	6	3 (50)	0.16	0.075	0.72	0.28	0.24	>0.99
	SAE	6	3 (50)	0	0 (0)	2	2 (33)	0.007	0.006	0.29	0.07	0.06	>0.99
Total	AE	42	6 (100)	23	8 (100)	48	6 (100)	0.06	0.06	0.73	>0.99	>0.99	>0.99
	SAE	9	4 (67)	0	0 (0)	3	3 (50)	<0.001	<0.001	0.15	0.03	0.015	>0.99

## **8. Intervention Suspension Related to Nutritional Counseling**

While we do not anticipate serious adverse events from medical nutrition therapy, we will suspend the nutritional interventions while participants are hospitalized, or if participants withdraw consent during the study. If participants wish to continue in the study after discharge, they may resume nutritional counseling with the approval of their treating physician. If participants develop significant dysphagia during the study and are deemed unable to swallow safely by a Speech Language Pathologist, even with dietary modifications, the study nutritional goals will be suspended until participants are able to obtain a feeding tube. Participants who receive a feeding tube will then receive Jevity 1.5 at 1.5 times their estimated total daily energy expenditure, regardless of the study arm to which they have been randomized.

## **9. STATISTICAL CONSIDERATIONS**

Statistical analyses will be performed by [name] of the MGH Biostatistics Center, who was the statistician on the High Fat/High Calorie vs. Optimal Nutrition in ALS clinical trial. Safety and tolerability will be assessed in all randomized participants, analyzed according to the treatment they actually received. Efficacy will be estimated from an intent-to-treat (ITT) sample, consisting of all randomized participants and analyzed according to their originally assigned treatment group regardless of adherence to that treatment. Secondary efficacy analyses will consider a per-protocol sample that adhered to their assigned treatment if this would differ from the mITT analysis for more than 10% of the sample. ALS, PD, and HD participants will be analyzed separated.

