### 2.1.7 Human Supporting Data

In brief, in the High Fat/High Calorie Diet versus Optimal Nutrition in ALS clinical trial[12], 24 ALS receiving percutaneous enteral nutrition were randomized 1:1:1 to 100% of caloric needs using Jevity 1.0 (control diet), approximately 125% of caloric needs using Jevity 1.5 (high carbohydrate/high calorie diet, HC/HC), or 125% of caloric needs using Oxepa which contains 55% fat calories (high fat/high calorie diet, HF/HC) (all Abbott Laboratories, Abbott Park, IL) and followed for four months. Total Daily Energy Expenditure was estimated based upon Measured Resting Energy Expenditure (MREE) multiplied by their physical activity level, or participants' pre-randomization nutrition requirements, whichever was greater. Participants and evaluating investigators were blinded to treatment assignment. Primary endpoints included adverse events (AE) and compliance rates.

[figure not shown]
Seven participants were randomized to the control diet, 9 to the high carbohydrate/high calorie diet, and 8 to the high fat/high calorie arms, although four participants (1, 1, and 2, respectively) withdrew after randomization but before starting study diet. There was no imbalance in treatment allocation across sites, and baseline demographics were similar among the three study arms. Control participants were more likely to discontinue the study diet due to adverse events

(three Cntl vs. zero HC/HC vs. one HF/HC) and less likely to complete the study on the intervention diet (17% vs. 88%, vs. 83%;  $p=0.03$  and  $0.08$  for the difference in tolerability between Cntls and the HC/HC and HF/HC groups, respectively).

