### **5.1.3 Standard Care**

The standard care group will receive routine nutritional counseling by a treating physician or nurse about the importance of avoiding weight loss at regular clinic visits, as is the standard of care in our Neurology clinics. All participants will be asked to complete and bring with them 4-day food records to each clinic visit.

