## **6.2 Definitions of Evaluations and Outcome Measures**

### **6.2.1 Primary Outcome Measures**

#### **6.2.1.1 Safety and Tolerability**

Safety will be evaluated using reporting of hospitalizations, deaths and other serious adverse events, and treatment discontinuations due to adverse events. Tolerability will be defined as the number of participants who do not decline nutritional counseling, i.e. the number of participants who complete the 6 months of counseling sessions in the in-person arm, or who enter at least 80% of the required data in the e-Health application arm. Tolerability will not be defined based on compliance with nutritional recommendations as compliance may be affected by other factors such as disease progression.

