### **9.1 *Safety and Tolerability***

All randomized subjects will be considered evaluable for tolerability and safety. Subjects lost to follow-up will be considered treatment failures at the time they drop out of the study. The data will be reviewed by the independent Medical Monitor, using the considerations here as guidelines. Their recommendation would then be reviewed by the Principal Investigator.

Safety data will be summarized by disease group and treatment group and reported to the independent Medical Monitor every 3 months during the study. Total numbers of adverse events will be compared within each disease group and among treatment groups using negative binomial regression and the proportion of participants experiencing each type of event by Fisher's exact test. Every 3 months the Medical Monitor will review cumulative study reports to determine if there has been an excess rate of serious adverse events in any of the arms. At two interim analyses, mortality rates will be compared, and one or both intervention arms may be terminated for one or more disease groups according to pre-determined stopping rules described below.

In the tolerability analyses, a subject will be regarded as a treatment success if he/she complies with at least 80% of the nutritional counseling sessions, or enters at least 80% of the required electronic data.

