### **9.3 *Sample size calculation:***

Using the component estimates from weight data collected in the clinical trial of Ceftriaxone in ALS [13] the effective standard deviation for rate of change in weight assuming weight assessments every 2 weeks, an annual 23% mortality rate, and 20% loss to follow-up is 0.98 kg/month. Given a sample size of approximately 150 ALS participants randomized 1:1:1 to the two interventions and standard care will provide at least 80% power to detect a true 0.75-kg/month difference between each intervention arm and the control arm over 24 wks at a two-tailed  $p < 0.027$  using Dunnett's method (testing superiority of each intervention over standard care). Based on a non-inferiority bound of 0.5 kg/month, the study will have at least 80% power to declare the e-Health intervention non-inferior to in-person consultation with an RD based on a one-tailed test at  $p < 0.05$  and assuming that the two interventions are in fact equivalent.

**Accrual Targets:** We intend to enroll 3-4 ALS subjects per week for the first 12 weeks, after which the rate will slow to 2-3 subjects/week, in order to accommodate return schedules and telephone visits. It should take approximately 12 months to enroll 150 participants at an average rate of 10 subjects per month. PD and HD subjects will be enrolled separately based upon funding and infrastructure availability.

**Treatment Discontinuation Rate Targets:** Subjects who discontinue treatment will be considered treatment failures in the tolerability analysis. However if there is an elevated discontinuation or study drop-out rate, it will reduce the power to detect a significant treatment difference for the primary outcome. The Steering Committee will analyze enrollment and discontinuation rates at pre-specified intervals and if it appears that fewer than 25 subjects per arm will complete the 6 month study, they may recommend increasing the enrollment times or stopping early for futility.

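### Safety and tolerability are grouped by treatment received, which is undefined for participants who never start or who stop, and is circular for tolerability

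*Protocol*

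**What the plan says.** Protocol section 9 sets two grouping rules. For safety and tolerability: "Safety and tolerability will be assessed in all randomized participants, analyzed according to the treatment they actually received". For efficacy, participants are "analyzed according to their originally assigned treatment group regardless of adherence to that treatment".

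Section 6.2.1.1 lists safety and tolerability among the primary outcomes and defines the second by refusal: "Tolerability will be defined as the number of participants who do not decline nutritional counseling". Its criteria, and the 80% rule in section 9.1, concern counseling sessions or app data only. Nothing is specified for standard care, which section 5.1.3 describes as follows: "The standard care group will receive routine nutritional counseling by a treating physician or nurse".

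Three further sentences deal with those who drop out or stop. Section 9.1: "All randomized subjects will be considered evaluable for tolerability and safety", and "Subjects lost to follow-up will be considered treatment failures at the time they drop out of the study". Section 9.3: "Subjects who discontinue treatment will be considered treatment failures in the tolerability analysis".

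The section 9.5 stopping rule compares survival in each intervention arm with the standard care arm by logrank test and does not state whether arms are as assigned or as received. Survival as an outcome uses the ITT sample (Protocol section 9.4; SAP tertiary outcome 2). The SAP summarizes safety by treatment group without further definition. It measures tolerability by the number of interactions and the time to the last one, and names no analysis group for it.

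**The concern.** Grouping by treatment received works when treatment is a discrete exposure and the outcome is something else. Here the tolerability outcome is whether the participant took the treatment. If uptake decides both the outcome and the group, the denominator depends on the outcome.

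The participants affected are those assigned to counseling or the app who take up none of it. Routine clinic advice is the comparator, so the plan's wording allows them to be classed as having received standard care, where they cannot be scored for tolerability. Participants who start and then stop are also unclassified, as are those whose intervention is suspended under section 8.

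For adverse events, regrouping would replace a randomized comparison with one that depends on uptake. Section 9.1 has the Medical Monitor review safety every 3 months, and an arm can be terminated under section 9.5, so the grouping bears on conduct of the trial as well as on reporting.

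**Working it through.** The plan states no figure on this point, so there is none to reproduce. The check sets the provisions side by side and then sizes the two readings under labelled assumptions.

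**1. What each provision settles**

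| Provision | Who counts, and how | In which arm |
|---|---|---|
| Section 9, safety and tolerability | all randomized | treatment received, undefined |
| Section 9, efficacy | all randomized | assigned |
| Section 6.2.1.1 | declining counseling is the failure | not stated |
| Section 9.1 | all evaluable; lost to follow-up are failures | not stated |
| Section 9.3 | discontinuations are failures | not stated |
| Section 9.5 | logrank, each intervention arm vs standard care | not stated |
| Section 9.4 and SAP tertiary outcome 2 | survival or mortality as an outcome | ITT |
| SAP, safety | summarized by treatment group | not defined |
| SAP, tolerability | engagement, length of involvement | not stated |

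The failure rules say what a non-adherent participant is. Only section 9 says where participants are counted for these outcomes, and it says by receipt. Because standard care has no tolerability criterion, a failure placed there has no meaning. The failure rules make sense only if the participant stays in the assigned arm.

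**2. Tolerability under the two readings**

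Assumptions, not in the documents: a share q of an intervention arm never starts, and a further o = 20% of the arm fails for other reasons.

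- Kept in the assigned arm: success = 1 − q − o.
- Moved out: success = (1 − q − o) / (1 − q).

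| q | Kept | Moved out | Difference (points) |
|---|---|---|---|
| 2% | 78% | 0.78/0.98 = 79.6% | 1.6 |
| 5% | 75% | 0.75/0.95 = 78.9% | 3.9 |
| 10% | 70% | 0.70/0.90 = 77.8% | 7.8 |
| 20% | 60% | 0.60/0.80 = 75.0% | 15.0 |

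With 50 per arm (150 ALS participants randomized 1:1:1), applying the same q to both intervention arms would enlarge the standard-care group from 50 to 52, 55, 60 or 70.

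**3. Adverse events under the two readings**

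Assumptions: equal arms; event risk 20% in standard care (it cancels below); a true risk ratio of 1.5 among starters; never-starters at k times the standard-care risk; both intervention arms lose share q.

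- As assigned: RR = 1.5(1 − q) + kq.
- Moved to standard care: RR = 1.5(1 + 2q) / (1 + 2qk).

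| q | k = 1, assigned | k = 1, moved | k = 2, assigned | k = 2, moved |
|---|---|---|---|---|
| 5% | 1.475 | 1.50 | 1.525 | 1.38 |
| 10% | 1.45 | 1.50 | 1.55 | 1.29 |
| 20% | 1.40 | 1.50 | 1.60 | 1.17 |

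If never-starters are at higher risk, moving them hides harm. If they carry the same risk as standard care, moving them recovers the assumed 1.50 and the as-assigned ratio is diluted. The direction therefore cannot be stated in advance.

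**The case against.** The strongest reply is that no provision moves anyone to standard care. Section 6.1.4 gives a right to refuse counseling and continues follow-up, without reassignment. Treatment received can equally be read so that any contact with the assigned intervention keeps a participant in that arm. Read with sections 6.2.1.1, 9.1 and 9.3, refusers stay where they are as failures and the tolerability shift is zero. Never-starters should also be few: randomization occurs at the screening/baseline visit, and dietitian guidance and written goals belong to baseline, although section 6.1.1 lets activities run up to 2 weeks later. Finally, grouping by receipt is a defensible choice for safety, and the SAP does not repeat the wording.

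Most of this stands, and it limits the point. It does not remove it, because the failure rules never name an arm, the sentence that does name one uses receipt, and the SAP is silent for tolerability. The SAP itself notes that many participants were lost to follow-up and that some only attended clinic, so classification is a practical question.

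A reader might go further and infer that the plan transfers refusers to standard care, so that tolerability is overstated and the interventions look safer. The documents do not say that, and the safety direction depends on an unknown risk. Nor is the earlier feeding trial a usable rate. There, 4 of 24 participants "withdrew after randomization but before starting study diet", but that was enteral formula in feeding-tube patients, and one of the four was a control. A reader might also extend the point to survival as an outcome; section 9.4 and the SAP already place that in the ITT sample.

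**Conclusion.** The point holds as a defect of specification. For tolerability, grouping by receipt is circular whatever the refusal rate and conflicts with the evident intent of sections 9.1 and 9.3. Its numerical effect is conditional: about 4 to 15 percentage points upward with 5% to 20% never-starters, 20% other failures and never-starters moved out; zero if they are kept. All of those rates are assumptions.

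For adverse events and the section 9.5 comparison, the wording permits non-random regrouping of unknown size and direction. No bias in favour of the interventions is established.

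**What to change.** In Protocol section 9 and in the SAP:

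- Analyse tolerability by randomized arm, with participants who never take up, or who discontinue, the counseling or the app counted as failures in that arm.
- State that between-arm adverse-event comparisons and the section 9.5 logrank comparison use randomized arm.
- Add a supportive safety summary by exposure, defined as at least one counseling session or app entry.

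This takes about one sentence in section 9 and a matching statement in the SAP, with no new data collection. There are two costs. Reported tolerability may be lower. Including unexposed participants can also dilute a harm signal (1.40 to 1.475 against 1.50 in the k = 1 illustration), which is why the exposed-only summary should be kept.

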### **9.1 *Safety and Tolerability***

All randomized subjects will be considered evaluable for tolerability and safety. Subjects lost to follow-up will be considered treatment failures at the time they drop out of the study. The data will be reviewed by the independent Medical Monitor, using the considerations here as guidelines. Their recommendation would then be reviewed by the Principal Investigator.

Safety data will be summarized by disease group and treatment group and reported to the independent Medical Monitor every 3 months during the study. Total numbers of adverse events will be compared within each disease group and among treatment groups using negative binomial regression and the proportion of participants experiencing each type of event by Fisher's exact test. Every 3 months the Medical Monitor will review cumulative study reports to determine if there has been an excess rate of serious adverse events in any of the arms. At two interim analyses, mortality rates will be compared, and one or both intervention arms may be terminated for one or more disease groups according to pre-determined stopping rules described below.

In the tolerability analyses, a subject will be regarded as a treatment success if he/she complies with at least 80% of the nutritional counseling sessions, or enters at least 80% of the required electronic data.

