## **Interventions and Duration**

### **Administration of Intervention**

The goal of the two intervention arms (medical nutrition therapy using in-person counseling or using the e-Health Application) will be modest weight gain of 0.5-1 kg/month. Participants in the in-person nutritional counseling arm will receive an initial face-to-face nutrition counseling session according to a resource book outlining the general nutritional recommendations (see Appendix 1), as well as a personalized nutrition plan with daily caloric goals. They will then receive telephone monitoring of weight with additional telephone counseling as needed between return clinic visits. Home self-reported weights in both intervention arms will be verified at routine clinic visits. Patients in the in-person counseling arm will also receive in-person nutritional counseling at every clinic visit.

Participants in the e-Health arm will receive dietary guidance from the treating RD at the baseline visit including instruction in the completion of food records and weight monitoring using the e-Health App. They will be asked to enter their dietary intake and home weights every 2 weeks. The treating RD will also have access to the e-Health App data and will be able to modify the dietary recommendations of the application according to the recorded weights.

The standard care group will receive routine nutritional counseling by a treating physician or nurse about the importance of avoiding weight loss at regular clinic visits, as is the standard of care in our Neurology clinics.

A research coordinator will collect data on adverse events, disease progression, appetite and quality of life measures in all participants, including standard care participants at month 1 by telephone and at every clinic visit, approximately every 3 months. If participants are unable to make it to the clinic, the above measures will be collected by telephone interview. The total duration of the interventions will be 6 months.

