## **Statistical Methods**

Statistical analyses will be performed by the MGH Biostatistics Center. The primary and secondary efficacy outcomes of change in weight and caloric intake will be compared between the treatment groups using a shared-baseline linear mixed model for correlated, longitudinal assessments of weight with fixed effects of time and the treatment x time interaction and age, gender, and baseline dysphagia and their interactions with time included as covariates and random participant specific intercepts and slopes.

Safety data will be summarized by treatment group and reported to an independent Medical Monitor every 3 months during the study. Total numbers of adverse events will be compared between groups using negative binomial regression and the proportion of participants experiencing each type of event by Fisher's exact test.

In the tolerability analyses, a subject will be regarded as a treatment success if he/she complies with at least 80% of the nutritional counseling sessions, or enters at least 80% of the required electronic data.

Sample size calculation: Using the component estimates from weight data collected in the clinical trial of Ceftriaxone in ALS [13] the effective standard deviation for rate of change in weight assuming weight assessments every 2 weeks, an annual 23% mortality rate, and 20% loss to follow-up is 0.98 kg/month. Given a sample size of 150 ALS participants randomized 1:1:1 to the two interventions and standard care will provide at least 80% power to detect a true 0.75-kg/month difference between each intervention arm and the control arm over 24 wks at a two-tailed  $p < 0.027$  using Dunnett's method (testing superiority of each intervention over standard care). Based on a non-inferiority bound of 0.5 kg/month, the study will have at least 80% power to declare the e-Health intervention non-inferior to in-person consultation with an RD based on a one-tailed test at  $p < 0.05$  and assuming that the two interventions are in fact equivalent.

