- 3) Quality of life as measured using the PROMIS SF v1.1 will be compared between the treatment groups using a shared-baseline linear mixed model for correlated, longitudinal assessments of PROMIS with fixed effects of time and the treatment x time interaction and age, gender, duration of disease and their interactions with time included as covariates and random participant specific intercepts and slopes.

Safety data will be summarized by treatment group. Total numbers of adverse events, categorized by organ system, will be compared between groups using negative binomial regression and the proportion of participants experiencing each type of event by Fisher's exact test.

Tolerability will be measured in two ways:

- 1) The amount of engagement that participants exhibited as measured by the number of interactions they had with a dietitian and the number of times that they interacted with the app,
- 2) The length of trial involvement as measured by the time to the last interaction with a dietitian (in-person or by App). Many participants were lost to follow-up (need to make sure documented). Participants who came to clinic visits only (seeing RD) but

did not engage otherwise, their last date of engagement is recorded in the Final Disposition form under "loss to follow-up"

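### Adverse-event totals are compared by negative binomial regression with no term for observation time, so an arm observed for less time would appear to have fewer events

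*Protocol*

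**What the plan says.** The AE model is described in three places. The précis (Statistical Methods) has: "Total numbers of adverse events will be compared between groups using negative binomial regression". Protocol 9.1 has: "Total numbers of adverse events will be compared within each disease group and among treatment groups using negative binomial regression". The SAP adds a split by body system: "Total numbers of adverse events, categorized by organ system, will be compared between groups using negative binomial regression". Each pairs the model with Fisher's exact test on the proportion of participants with each type of event. None mentions exposure, person-time, an offset or a rate.

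Other provisions decide how long each person is observed for AEs:

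- Safety set (9.1): "All randomized subjects will be considered evaluable for tolerability and safety".
- Observation window (10.5): from consent until the person's participation ends.
- Planned length (précis): "The total duration of the interventions will be 6 months". Section 6.1.5 adds an AE telephone call to everyone one month after the final visit, giving about 7 months.
- Expected attrition (9.3): the effective standard deviation assuming "an annual 23% mortality rate, and 20% loss to follow-up is 0.98 kg/month". Neither attrition figure is split by arm.
- After stopping (6.1.4): telephone visits are to supply AE data for the primary safety analysis, and all attempts are to be made to keep following these participants.
- Contacts (Table 1 and its first footnote): every arm has a coordinator call at month 1 and clinic visits at months 3 and 6. The dietitian also records AEs at each telephone contact, in the in-person arm only.

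**The concern.** A negative binomial model for a total, without an exposure term, treats a participant watched for two months as if watched for six. Fewer recorded events then reflect both the event rate and the length of observation, and the two cannot be separated. Fisher's test on proportions has the same weakness.

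Safety is one of the primary outcomes (6.2.1.1). The arms are open-label and ask very different amounts of participants, so equal drop-out cannot be taken for granted. If one arm were observed for less time, its AE burden would look lighter for that reason alone. The plan does allow for follow-up time elsewhere: logrank tests in the mortality stopping rule (9.5) and a Cox model for survival (9.4). In 9.1 the Medical Monitor is to look for an excess rate of serious events, but no denominator is defined.

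**Working it through.** The documents give no expected AE ratio, power or alpha for this comparison, so there is no plan figure to reproduce. The check asks how far the apparent ratio moves when the true rates are equal.

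**Inputs from the protocol.** About 50 ALS participants per arm (150 randomized 1:1:1), annual mortality 23%, planned period T = 6 months, or 7 with the last AE call.

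**Assumptions.** The period for the 20% loss is not stated; it is taken as 6 months. Loss by arm is not given, so the 6-month loss d is varied from 10% to 50%. Mortality is equal in all arms, drop-out times are exponential, and the AE rate is constant over time.

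**Step 1: mean observation time per arm.**

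Monthly hazard of leaving: h = −ln(0.77)/12 − ln(1 − d)/6. The mortality part is 0.2614/12 = 0.0218.

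Mean observation time: m = (1 − exp(−hT))/h.

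Example, d = 10%, T = 6: h = 0.0218 + 0.1054/6 = 0.0393; exp(−6h) = √0.77 × 0.90 = 0.7897; m = 0.2103/0.03934 = 5.34 months.

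| 6-month loss | Mean months observed (T = 6) |
|---|---|
| 10% | 5.34 |
| 20% | 5.05 |
| 30% | 4.75 |
| 40% | 4.43 |
| 50% | 4.09 |

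**Step 2: apparent AE ratio without an offset.** With equal constant rates, expected totals are proportional to m, so the ratio is m(higher loss)/m(lower loss).

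| Loss by arm | T = 6 | T = 7 |
|---|---|---|
| 20% vs 20% | 1.00 | 1.00 |
| 10% vs 30% | 4.749/5.344 = 0.889 | 5.339/6.119 = 0.873 |
| 10% vs 40% | 4.429/5.344 = 0.829 | 4.928/6.119 = 0.805 |
| 10% vs 50% | 4.088/5.344 = 0.765 | 4.498/6.119 = 0.735 |

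**Step 3: effect on the test.** Simulated gamma-Poisson counts: 50 per arm, 500 runs per setting, T = 6, assumed dispersion 0.5, assumed rates of 0.5 and 1.75 AEs per month, equal between arms. False-positive rates are at nominal 5%, with simulation error of about 1 point.

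| Loss by arm | Ratio, no offset | False positives | Ratio, offset | False positives |
|---|---|---|---|---|
| 20% vs 20% | 0.99–1.01 | 5–6% | 1.00–1.01 | 5–6% |
| 10% vs 30% | 0.89 | 9–12% | 1.00 | 6–7% |
| 10% vs 50% | 0.77 | 21–27% | 1.00–1.01 | 6–7% |

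**Step 4: when the constant-rate assumption fails.** A further run (400 per setting, 2 AEs per 6 months, dispersion 0.5) put half of all AEs in month 1, as might happen when a diet is started.

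| Loss by arm | Ratio, no offset | False positives | Ratio, offset | False positives |
|---|---|---|---|---|
| 10% vs 30% | 0.92 | 5% | 1.04 | 6% |
| 10% vs 50% | 0.85 | 14% | 1.11 | 8% |

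The offset is still nearer to 1, but it now errs in the opposite direction.

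**The case against.** Several stronger readings are tempting, and the documents do not support them.

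- **That follow-up is unequal between arms by design.** The 23% and 20% are overall sample-size assumptions. With equal loss the ratio is 1.00. The arm-specific splits above are illustrations.
- **That the SAP shows lost AE observation.** Its remark "Many participants were lost to follow-up" sits under tolerability, which is measured by engagement with the dietitian or the app. The text that follows it files under the same label people who came to clinic visits but did not otherwise engage. AEs are collected at clinic visits in every arm, so the remark does not measure missing AE time.
- **That stopping counseling ends AE follow-up.** Section 6.1.4 provides telephone AE follow-up after stopping. This would shrink any gap, though not for people who cannot be reached or who refuse contact.
- **That the plan excludes an offset.** It is silent. A negative binomial model can carry one, but the stated outcome is a total, and an analyst following the text would fit raw counts.
- **That the offset makes the arms comparable.** It assumes a roughly constant rate (Step 4). It also leaves untouched the extra AE capture at dietitian calls, which could make the in-person arm look less safe.

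It is also fair to say that importance is limited. Section 6.2.1.1 evaluates safety through hospitalizations, deaths, other serious events and discontinuations due to AEs. No success or stopping rule uses the AE total, and the mortality rule uses logrank tests, which handle censoring.

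These points limit the size and certainty of the problem. None is a reason to leave observation time out of the model.

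**Conclusion.** The point holds as a conditional weakness. As written, the comparison of totals is biased whenever mean AE observation time differs between arms, and nothing in the plan corrects for it. Whether it does differ cannot be judged from the documents. Under equal constant rates, equal mortality and exponential drop-out, the apparent ratio over 6 months runs from 1.00 (equal loss) through 0.889 (10% vs 30%) to 0.765 (10% vs 50%). The false-positive rate at nominal 5% rises to about 9–12% and 21–27% in the last two cases, given the assumed event rates and dispersion. With events concentrated early, the distortion is smaller and the offset is better but not exact. This is a worthwhile, inexpensive improvement to a supporting safety analysis; it does not undermine the trial's main conclusions.

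**What to change.** In protocol 9.1, the précis and the SAP, specify negative binomial regression with the log of AE observation time as an offset, and report rate ratios with AEs per person-month by arm. The same offset applies to each body-system model.

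Define observation time as randomization to the last contact at which AEs were sought, including the call one month after the final visit, and count only events from randomization onward so that numerator and denominator match. The later six-monthly calls in 6.1.5 record vital status, weight and procedures, and should not extend the window. State a rule for anyone with no AE contact after randomization, since log of zero is undefined.

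Add a sensitivity analysis restricted to the AE contacts common to all arms: the month-1 coordinator call, the month-3 and month-6 visits, and the call after the final visit. Tabulate AE observation time by arm, so that readers can see whether it differed.

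The cost is a sentence or two in each document and one extra model run. The one real task is to confirm that last AE-contact dates exist for all three arms: the SAP itself notes that documentation of loss to follow-up still needed checking, and section 6.1.2 provides for recording counseling sessions rather than AE contacts in every arm.
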